9.6.1 Allocation of Study Medication

Once an antibiotic for an acute infection has been prescribed to a SU who has provided advanced consent to participate in the study, the SU will be re-assessed against the following exclusion criteria. All criteria must be answered no for a SU to be allocated study medication (i.e. randomised)

Exclusion criteria

- Previously been allocated study medication
- Service User's stool pattern is diarrhoea (defined as 3 or more stools at BSC type 5-7 within 24 hours)
- Severely immuno-compromised, e.g. known severe neutropenia
- Has artificial heart valve in situ.
- Medical history of acute pancreatitis.
- Requires naso-jejunal feeding /nasogastric
- Currently has a colostomy.
- SU is taking a probiotic on a regular basis and is unwilling to discontinue use.

General Practitioners (GPs), visiting their SU, will assess the SU for Eligibility for Study Medication CRF to re-confirm their eligibility at the same time as they prescribe the antibiotic(s). In the event that re-confirmation of eligibility and randomisation authorisation has not been obtained at the time of GP visit, the CHS will be trained and encouraged to alert the researchers by telephone or by fax within 24 hours of the SU being issued with a prescription. The RNs may assess eligibility; however the final approval for randomisation of the SU will be from a responsible clinician at the SU's general practice obtained either by fax from the RN or by a personal visit by a researcher to the GP surgery. When the SU has been confirmed as eligible, the next sequentially numbered study medication pack will be allocated to the SU.

In the event that the researchers cannot obtain GP approval for randomisation and prescription completion for the study medication within 72h, the SU will be monitored until such time they are prescribed a further antibiotic. At this time point the same procedure as described above will be followed.

9.6.2 Unblinding participants.

In the event that the SU needs to be unblinded the care home staff are directed to contact the PAAD team on [name]. The PAAD unblinding SOP will be followed to un-blind the participant and in this case the un-blinding of randomised SUs can only be carried out by the QA Manager at SEWTU.

9.7 Screening, enrolment and randomisation logs

A screening, enrolment and randomisation log will be prepared for each care home and will be populated from the care home list of current residents. The log will record when SU are approached, whether they were consented and subsequently randomised and any reasons for a SU being excluded, not consenting or not being randomised. This information will be recorded so that any bias from differential recruitment can be detected. An anonymised screening log will be faxed or a photocopy sent to the PAAD TM at regular intervals to allow monitoring of recruitment progression.

10 Withdrawal & loss to follow-up

10.1 Withdrawal

SUs may withdraw consent for participation from any aspect of the study at any time. The care of SUs will not be affected by declining to participate or withdrawing from the study.

If the SU does not have capacity to consent, their personal/professional legal representative may withdraw them from any aspect of the study at any time, without their future clinical care being affected. The Investigator or the SU's GP may withdraw SUs from the study intervention at any time if he/she considers that the SUs health or

wellbeing is compromised by remaining in the study. The CHS/PAAD research nurse will notify SEWTU of the withdrawal of the SU by telephone as soon as possible, and arrangements made for the withdrawal form to be sent via fax (if possible). The TM will liaise with the CHS/PAAD research nurse to obtain the hard copy of the form at the next available opportunity.

A withdrawal CRF will be completed either:

- When a SU expresses their desire to withdraw from the study;
- When a SUs personal/professional legal representative expresses their desire for the SU to be withdrawn from the study.

Furthermore, if a SU initially consents but subsequently withdraws from the study the SU will be asked to decide whether they would:

- wish to withdraw from the study, but allow the data to be collected until the end of the study
- wish to withdraw from the study, but refuse to allow data to be collected until the end of the study
- wish to withdraw from study and require all data collected to date to be destroyed

A SU may withdraw or be withdrawn from the study intervention by the Investigator for the following reasons:

- Any alteration in the participants condition which justifies the discontinuation of the study intervention in the Investigator's opinion,
- Intolerance to the study medication.

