In the event that a personal/professional legal representative themselves loses capacity or dies during the study period, an alternative personal/professional legal representative will be contacted. If there is no one to represent the SU in the study, the SU will be excluded.

If the SU's own GP is the designated professional legal representative, an alternate GP within the same general practice, who is not involved in the conduct of the study, or the running or management of the care home, will be asked to act as their professional legal representative.

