12.2.2 SAEs

All SAEs and reactions must be reported immediately by the care home manager or a senior staff member to SEWTU. A completed SAE form for all events should be faxed to SEWTU within 24 hours of knowledge of the event (or the next working day) on [name]. A flowchart is provided in Figure 3 to aid in the reporting procedures.

Responsibility for the reporting of SUSARs and other SARs to the regulatory authorities (MHRA) and the REC are as follows:

- SUSARs which are fatal or life-threatening must be reported not later than 7 days after the sponsor is first aware of the reaction. Any additional relevant information must be reported within a further 8 days.
- SUSARs that are not fatal or life-threatening must be reported within 15 days of the sponsor first becoming aware of the reaction.

SAEs will be reported from the time a participant is randomised onto the study and for the 8 weeks follow up duration.

SAEs will be followed up by the PAAD team until they are resolved or the investigator assesses them as chronic or stable. The follow up and outcome of SAEs will be document in the appropriate CRF.

A list of all SARs (expected and unexpected) must be reported annually to the MHRA and REC.

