14.1 Randomisation

Randomisation will be carried out using random permuted blocks. Computer-generated random numbers will be produced to select a block of allocations from the set of all possible permutations of allocations (on a 1:1 ratio) given a particular block-size before the trial begins.

14.2 **Primary outcome measures**

The primary outcome is the occurrence of at least one episode of AAD during the eight weeks following randomisation. AAD is defined as three or more loose stools (defined as a 5 – 7 on the BSC) in a 24 hour period following a period of normal stool consistency.

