15.1 Main analysis

For the primary analysis, a logistic regression model will be constructed with AAD during eight week follow-up (Yes/No) as the dependent variable and study arm (probiotic/placebo) as an explanatory variable. The analysis will be adjusted for:

- The potential clustering of SUs within care homes via multilevel analysis
- Potential, pre-specified confounding/risk factors as specified in the Statistical Analysis Plan

The primary analysis will be based on the intention to treat principle.

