15.3 Data storage & retention

All data will be kept for 15 years in line with Cardiff University's Research Governance Framework Regulations for clinical research. This data will be stored confidentially on password protected servers maintained on the Cardiff University Network.

Electronic data will be stored on fire-walled University computers, and only accessible to researchers involved in the study. All procedures for data storage, processing and management will be in compliance with the Data Protection Act 1998. All paper records will be stored in a locked filing cabinet, with keys available only to the trial management team. The Trial Statistician will carry out analysis. All essential documents generated by the study will be kept in the trial master file.

16 Study closure

The end of the study will be considered as the date on which the last participant has completed their follow-up assessment.

For the purpose of regulatory requirements the end of the study is defined as the end of the follow-up period of the last recruited SU. For the purpose of the research ethics committee the study end date is deemed to be the date of last data capture.

17 Regulatory and ethical issues

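### Section 10.1 lets a withdrawing randomised resident have all data destroyed, which contradicts the retention rule, undermines intention to treat and has no stated exception for safety records

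*Protocol*

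**What the plan says.** Section 10.1 of the protocol asks a resident who consented and later withdraws to choose among three courses. The first lets data collection continue to the end of the study. The second is to "wish to withdraw from the study, but refuse to allow data to be collected until the end of the study"; it says nothing about removing what is already held. The third is to "wish to withdraw from study and require all data collected to date to be destroyed". It is offered to every withdrawing resident, whether or not randomised, and names no type of record that is exempt.

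Four other parts of the protocol bear on this:

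- Section 14.2: "The primary outcome is the occurrence of at least one episode of AAD during the eight weeks following randomisation".
- Section 15.1: "The primary analysis will be based on the intention to treat principle". The model is a logistic regression adjusted for pre-specified risk factors and for "The potential clustering of SUs within care homes via multilevel analysis".
- Section 15.3: "All data will be kept for 15 years". Section 17.5 is looser and sets 15 years after closure as an upper limit.
- Sections 12.2 and 12.2.2: all serious adverse events from randomisation to week eight are reported and then followed until resolved, chronic or stable, and "A list of all SARs (expected and unexpected) must be reported annually to the MHRA and REC".

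No section says how the third choice fits with these rules.

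**The concern.** Destroying everything collected on request cannot be squared with keeping everything for 15 years. One of the two statements has to give way, and the protocol does not say which.

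For the primary analysis, the problem is what remains of a randomised resident. Once the file is destroyed there is no diarrhoea outcome, no baseline covariate and no care home identifier. The resident cannot enter the multilevel model and cannot be imputed from baseline data. The statistical analysis plan, which is not at hand, could not repair this, because no analysis rule restores data that no longer exist.

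The loss need not be random. The primary outcome is itself unpleasant, and section 12.3 lists bloating, flatulence and rash as expected reactions to the sachets. A resident or representative may withdraw because of either, so erasure may depend on the outcome, and through side effects it may differ by arm. The same records carry safety information in a trial that section 17.4 places somewhat above the risk of standard care.

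**Working it through.** **Comparing the sections.** The contradiction is one of text and rests on no figure.

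| Rule | Requires | If a randomised resident takes the third choice |
|---|---|---|
| 15.3 retention | all data kept 15 years | directly contradicted |
| 15.1 intention to treat, multilevel logistic model | outcome, covariates and care home for each randomised resident | none available; allocation perhaps on the randomisation list |
| 12.2, 12.2.2 safety | reporting, follow-up, annual list of reactions | no exemption stated; reports already sent may survive |

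**Scale: inputs.** Section 14.4 gives 25% incidence on placebo, a 50% relative reduction (so 12.5% on probiotic), the 5% level, 80% power, 200 per arm and a 20% loss allowance. A two-sided test is assumed, since sidedness is not stated.

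**The plan's own figure.** With mean proportion 0.1875,

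n per arm = [1.96·√(2·0.1875·0.8125) + 0.8416·√(0.25·0.75 + 0.125·0.875)]² / 0.125² = (1.0819 + 0.4586)² / 0.015625 ≈ 151.9, so 152.

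That is 304 in total, and 304/0.8 = 380. With a continuity correction it is 168 per arm, 336 in total, and 336/0.8 = 420. The stated 400 lies between the two and is not reproduced exactly by either. After the full 20% loss, 200 × 0.8 = 160 per arm remain, and the uncorrected power is 82.0%.

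**Power if a share of each arm is erased in addition to the 20% loss.** The share is an assumption; the protocol gives none.

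| Erased per arm | Residents of 400 | Analysed per arm | Power |
|---|---|---|---|
| 1% | 4 | 158 | 81.5% |
| 2% | 8 | 156 | 81.1% |
| 5% | 20 | 150 | 79.5% |
| 10% | 40 | 140 | 76.7% |

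**Possible bias.** Suppose a 12.5-point reduction is seen among retained residents, a fraction d of each arm is erased, and the erased outcomes are unknown. Ignoring other losses, the reduction in the full randomised set lies in 12.5(1 − d) ± 100d points:

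- d = 1%: 12.375 ± 1, or 11.4 to 13.4 points
- d = 5%: 11.875 ± 5, or 6.9 to 16.9 points
- d = 10%: 11.25 ± 10, or 1.3 to 21.3 points

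These are extreme bounds, not expected bias. They show that inflating the sample by 20% replaces numbers but does not settle what the erased outcomes were.

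**The case against.** Much can be said for the protocol here. The trial is double-blind with a matched placebo, few residents may ask for destruction, and a 20% loss is already allowed for. The choice also covers residents who withdraw before randomisation; section 14.4 assumes about a third of those enrolled never reach it, and for them erasure has no bearing on intention to treat. Stopping the sachets for intolerance or a changed condition is listed separately in section 10.1 and does not of itself lead to destruction. All of this stands. It narrows the point to randomised residents and makes the likely frequency low, but it does not remove the contradiction.

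Four stronger readings are tempting, and the documents do not support them.

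- *Intention to treat becomes impossible.* The allocation is held in the randomisation file (section 9.6), and randomisation status is on the care home log (section 9.7). If these survive, affected residents can be counted by arm and worst-case bounds given. What is lost is the analysis of their outcomes.
- *Safety data disappear.* Section 12.2.2 sends serious event forms to the trials unit within 24 hours or the next working day, and section 12.2.3 passes them to the manufacturer. Submitted reports may well survive. The defect is that no exception is stated.
- *The effect estimate and power collapse.* Starting from 50/200 against 25/200, erasing 10 diarrhoea cases from placebo only gives 40/190 and a relative risk of 0.125/0.2105 = 0.59. Nothing in the protocol suggests that diarrhoea would prompt erasure in one arm only. Erasing 20% of cases in both arms gives 40/190 against 20/195, a relative risk of 0.49, with power 83.3% compared with 89.6% at 200 per arm. Even the placebo-only case gives 62.0% on its own denominators; a lower figure comes from combining those rates with 160 per arm.
- *Section 9.5.2 is a second exclusion after randomisation.* It says "If there is no one to represent the SU in the study, the SU will be excluded", but only after an alternative personal or professional representative has been sought, and it does not say that data are removed. It needs a clarification and no more.

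It can also be argued that the choice respects the rights of a vulnerable group and that a one-line exception for safety and essential records would be enough. Such a line would settle the safety point and could reconcile section 15.3, but it would leave the loss of randomised outcomes untouched.

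**Conclusion.** The point holds in a limited form. For randomised residents, section 10.1 as written contradicts section 15.3, undermines the primary analysis promised in section 15.1 for anyone who takes the third choice, and lacks an exception for the records that section 12 requires. That conclusion rests on the text alone.

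The practical size is unknown and probably small. On the uncorrected two-sided calculation, erasure unrelated to outcome costs about 2.5 percentage points of power at 5% per arm (82.0% to 79.5%). The weightier risk is loss related to outcome, and it is irreversible: once records are destroyed, neither its direction nor its extent can be examined. The matter should be corrected, and before any randomised resident's data are destroyed.

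**What to change.** In section 10.1, limit the third choice to residents who have not been randomised. For randomised residents, state that withdrawal stops further collection to the extent they wish, and that data up to that date, including serious adverse event and essential records, are retained for the period in section 15.3 and analysed as randomised. The second choice already provides for stopping collection. Make the information sheets and consent forms say the same.

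As a minor clarification in section 9.5.2, say that exclusion for want of any representative does not remove data already collected from a randomised resident.

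The cost is a protocol and information-sheet amendment needing ethics approval, and one fewer choice for a withdrawing randomised resident. The right to withdraw at any time is unchanged.

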10.2 Loss to Follow-up

Care home staff will be requested to notify the PAAD trial manager of any participant who moves out of their care home during the 8 week follow up period.

11 Study Intervention

There are two intervention arms on the PAAD Study Stage 2 RCT. The active arm is the nutritional supplement VSL#3 probiotic which contains approximately 450 billion live lactic acid bacteria and bifidobacteria, together with maltose and silicone dioxide. There are eight different strains of potentially beneficial bacteria: *Streptococcus thermophilus, Bifidobacterium breve, Bifidobacterium longum, Bifidobacterium infantis, Lactobacillus acidophilus, Lactobacillus plantarum, Lactobacillus paracasei and Lactobacillus delbrueckii subsp. Bulgaricus.*

The matching Placebo arm of the study consists of (4.4g) of freeze dried powder 4.4g, matched for taste, consistency, odour and colour. The use of an indistinguishable placebo will avoid the biasing of identification and assessment of outcomes.

11.1 Dispensing Study medication

SUs who have provided advanced consent, have been prescribed antibiotic(s) and remain eligible for study medication, will be randomised to receive either the active probiotic or the placebo. At this point, the SU will be allocated study medication (see 9.6.1 for details on allocation of study medication). Study medication should commence ideally on the day the antibiotic was started, and no later than 72 hours after.

The SU should be given one sachet twice a day. The sachet should be opened and the contents stirred into cold water or any non-fizzy drink or cold food and consumed immediately. The study medication should be given in between the antibiotic therapy and not in conjunction with the antibiotic.

Accidental contamination with small numbers of the probiotic bacteria by participants allocated to the placebo arm due to the probiotic being prepared in the same environment may occur; however the level of airborne contamination is likely to be minimal. A designated area for the dispensing and preparation of the study medication, will be discussed with each care home while all staff will be guided in preparation and administration of the study interventions to minimise cross-contamination. Plastic pots (if required) will be provided to reconstitute the study preparation before consumption.

11.2 Supply, packaging and reconciliation of study materials

Primary bulk manufacturing, labelling and delivery of both VSL# 3 and placebo will be performed by Actial Farmaceutica Lda, Portugal. Actiel, will grant the licence of use of these products in the UK and also provide primary Qualified Person (QP), release. Bulk batches will be delivered to St Mary's Pharmaceutical Unit (SMPU), which is a pharmaceutical

manufacturing facility and part of the Cardiff and Vale University Health Board and stored according to manufacture conditions.

SMPU will label and pack individual intervention medication packs. Study medication will be packed into primary and secondary packaging. Firstly each individual sachet, (primary pack), containing probiotic or placebo, will be labelled stating 4.4g VSL[#]3 or matching placebo, for single use. The label will state 'for clinical trial use only', and designed in accordance with annex 13.

Sachet will be then be packed and sealed inside a card board box, (secondary pack), which again will be labelled according to annex 13 and will include enough study medication for a course for one participant.

An initial starter pack will be sent to care homes, which will consist of 6 study medication packs. Each medication pack will consist of 46 sachets enough for 21 days of study medication along with 4 extra to be used in case of spillage in preparation. Thereafter when the care home study medication levels reach 3 study mediation packs remaining, a PAAD Study Medication Requisition Form (requesting 6 study medication packs) will be completed and sent to the PAAD Trial Manager. Upon receipt of a PAAD Study Medication Form, the PAAD team will fax to SMPU who will arrange for a courier who will deliver 6 study medication packs via cold storage conditions within 48 hours.

The SmPC for VSL#3 states that the product should be stored in a refrigerator (2-8°C), therefore, upon receipt of study medication by the CHS, the PAAD reconciliation form will be updated and all study medication will be either stored in a PAAD designated fridge or within a designated area of an existing fridge within the care home. The temperature of this fridge will be regularly monitored using minimum/maximum calibrated temperature probe by designated CHS/RN. CHS will maintain temperature monitoring logs.

All unused sachets of the study medication (not included within the viability testing – see section 11.7) will also be disposed off according to local care home procedures and logged within the reconciliation form.

11.3 Dose modification for toxicity

If bloating is experienced, it is recommended to reduce the daily intake to half to allow for adjustment. If the participant continues to be uncomfortable the study medication should be stopped.

11.4 Pre-medication

There are no listed pre-medication for VSL#3.

11.5 Interaction with other medications

VSL#3 is believed to be compatible with all types of medications.

11.6 Permitted concomitant medications

All concomitant medications are permitted.

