8.1 Inclusion criteria at consent

- Resident in a care home for 24 hours or more, with a minimum planned period of residential care of 1 month.
- Able to provide informed consent or have a personal legal representative who can provide consent for inclusion.
- If the SU takes a regular probiotic but chooses to discontinue the probiotic

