8.2 Exclusion criteria

- Severely immuno-compromised, e.g. known severe neutropenia
- Has artificial heart valve in situ.
- Medical history of acute pancreatitis.
- Requires naso-jejunal feeding /nasogastric feeding Currently has a colostomy.
- SU without capacity already receiving a probiotic

9 Recruitment and randomisation of Service Users

Following site initiation, the care home will aim to enrol all eligible SUs at that site. At this point, SUs (or their representatives) will be asked to provide consent to be monitored for up to one year and to be randomised to receive probiotic or placebo should they be prescribed antibiotics for acute infection in the course of routine care during this period.

There are likely to be two types of SUs who are eligible to join the study; those who have capacity and are able to consent for themselves and those unable to consent for themselves (lack capacity). Consent procedures will differ according to the mental capacity of the SU. ICH GCP trained senior care home staff/care home nursing staff or trained PAAD study RNs, will be responsible for consenting SUs or their personal/professional legal representatives.

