12.2.1 Non serious AR/AEs

Since the study intervention is defined as a probiotic, which is a nutritional supplement, containing known species of live bacteria that are included in foods and commercially available, we do not request all adverse events (AEs) be reported. All expected adverse reactions will be recorded using the symptoms (Illness severity and symptoms CRF) section in the Daily Diary.

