13.4.5 Medication use

A record of the medication used post randomisation for the 8 weeks of follow up will be collected.

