13.4.6 Stool sampling

Diagnostic stool samples will be collected only at times when diarrhoea occurs during follow up and a second sample will be collected if diarrhoea continues for greater than 48 hours. Diarrhoea, for the purposes of this study, is defined as 3 or more loose stools at BSC type 5 – 7, in a 24 hour period, following a period of normal stool consistency. Sampling will be carried out by a CHS / study research nurse. The sample will be put into containers provided by the study team. This container must be labelled with the participants ID number, initials and date of birth and sent by 1^{st} Class Royal Mail using Post Office approved SafeboxesTM, a method that meets legal requirements. The sample must be sent within 48 hours of taking the sample, in order to be analysed within 72 hours. The sample will be sent to the Public Health Wales Microbiology laboratory for the determination of microbial content, speciation of *C. difficile* culture, toxins A and B and as well as screening for carriage of antibiotic resistant bacteria. Any cultured *C. diff* isolates will be ribo-typed, toxin tested, and have antimicrobial sensitivity testing done, as well as screening for carriage of antibiotic resistant bacteria. All isolates will be retained and stored at -70°C.

The research team will receive results of study diagnostic stool sample analyses from the Microbiology laboratory.

		Defere	At time of	At time of antibiotic			F	ollow Up (wee	o Period ks)			
	Data Type	Berore study recruitment begins	consent	prescribed/ eligibility checked and confirmed	1	2	3	4	5	6	7	8
1.	Care Home	X										
2.	Eligibility for enrolment		Х									
3.	Eligibility for Study Medication			X								
	a) Medical information			X								
4.	Follow up diary											
	a) Study medication and antibiotic adherence				D	D	D	D				
	 b) Illness severity and symptoms 				D	D	D	D	D	D	D	D
	c) Stool monitoring				D	D	D	D	D	D	D	D
	d) Additional Medication				W1	W1	W1	W1	W1	W1	W1	W1
	e) Quality of life				W2	W2	W2	W2	W2	W2	W2	W2
	f) Healthcare resource use											E
5.	Diagnostic Stool Sample				I<			as req	uired			>l
6.	Withdrawal		I<			as	required					>l
7.	SAE				I<			as req	uired			>l

Table 1 – CRF schedule

D = Questions are to be completed on a daily basis

W1 = Questions should be completed on weekly basis for that week

W2 = Questions should be completed at the start of the week based on that day

E = Questions are to be completed at the end of the 8 week follow-up

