14.4 Sample size

A total of 400 SUs (200 per arm) will need to be randomised in order to achieve 80% power, at the 5% level, to detect a 50% relative reduction in the incidence of antibiotic associated diarrhoea in those given probiotic intervention alongside antibiotic treatment, compared to placebo alongside antibiotic treatment. This sample size has been adjusted for a 20% loss to follow-up/withdrawal.

Taking into consideration the results from the interim analysis performed in PAAD Stage 1 and a more recent interim assessment of antibiotic prescribing and AAD (from first antibiotic prescription), assuming an AAD incidence of 25% in the placebo arm (lower confidence limit quoted in Appendix 3), in order to randomise 400 SUs we will need to obtain advanced consent from at least 607 SUs (assuming 66% will be prescribed at least one course antibiotics during the 12 month monitoring period and subsequently randomised) and will need to approach approximately 1214 SUs in order to achieve this consent rate (assuming only 50% will provide consent). With an average of 60 SUs per home, we will need to recruit from a minimum of 21 care homes. In order to allow for care home drop-out, larger than anticipated withdrawals/drop-out/declines and smaller than anticipated care homes, we aim to recruit from 24 care homes.

15 Analysis

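### The probiotic restrictions are entry checks only: nothing bars a resident who was not a regular user from starting a non-study probiotic after allocation (low to moderate priority)

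*Protocol*

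**What the plan says.** Section 11.6 of the Protocol reads, in full: "All concomitant medications are permitted". It makes no exception.

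Non-study probiotics are restricted in three places:

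- Section 8.1, inclusion at consent: "If the SU takes a regular probiotic but chooses to discontinue the probiotic".
- Section 8.2, exclusion at consent: "SU without capacity already receiving a probiotic".
- Section 9.6.1, exclusion re-checked before study medication is allocated: "SU is taking a probiotic on a regular basis and is unwilling to discontinue use".

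Section 12.2.1 describes the study product as "containing known species of live bacteria that are included in foods and commercially available". Section 11.1 deals with contamination of the placebo arm, but only with accidental airborne contamination during preparation.

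On recording, Section 13.4.5 states: "A record of the medication used post randomisation for the 8 weeks of follow up will be collected". Table 1 (CRF schedule) lists a weekly form, "d) Additional Medication". Section 15.1 bases the primary analysis on intention to treat.

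**The concern.** The entry rules treat outside probiotic use as incompatible with the comparison: a regular user who will not stop cannot be randomised. After allocation no rule protects the same contrast. A resident who was not a regular user, or that resident's family, may begin a commercial probiotic the next day and remain fully compliant.

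The stake is dilution. The primary outcome is at least one AAD episode in eight weeks. If some placebo residents take an effective outside product before their first episode, the placebo rate falls towards the probiotic rate, and the intention-to-treat contrast shrinks with it. A null result would then be harder to interpret. Use that begins after a first episode cannot change the primary outcome, and use that begins late dilutes it less.

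**Working it through.** **1. Is there a bar anywhere?** Set side by side, the criteria in Sections 8.1, 8.2 and 9.6.1 each ask about a probiotic being taken when the check is made. Section 11.6 governs the period after allocation and excludes nothing. Starting a probiotic is not among the reasons for withdrawal in Section 10.1. Section 13.4.5 and Table 1 record medication but do not restrict it. No section bars a new start.

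**2. Inputs.** From Section 14.4: 200 per arm, 80% power, 5% level, 50% relative reduction, 20% loss, and "assuming an AAD incidence of 25% in the placebo arm". Evaluable per arm: 200 × 0.8 = 160. Assumed here: a two-sided test, no clustering, pooled-variance normal approximation. The share using an outside product (*c*) and its relative reduction (*e*) are assumptions, since the document gives neither.

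**3. The plan's own sample size.** For 25% against 12.5% the formula gives 152 per arm, and 2 × 152/0.8 = 380. With continuity correction it gives 168 per arm: 2 × 168/0.8 = 420, or 404 if inflated by 1.2 instead. The stated 400 is consistent with these.

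**4. Power formula.** With n per arm, rates p₁ and p₂, and p̄ their mean:

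power = Φ{[(p₁ − p₂)√n − 1.96√(2p̄(1 − p̄))] / √(p₁(1 − p₁) + p₂(1 − p₂))}

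No outside use: (0.125 × √160 − 1.96 × 0.5520)/0.5449 = (1.581 − 1.082)/0.5449 = 0.916, so power is 82.0%.

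**5. Outside use, fully effective (e = 0.50), taken from the start.** Placebo rate = 0.25 × (1 − c × e). In the worst case the probiotic arm stays at 12.5%. With equal use and proportional benefit, the probiotic rate is half the diluted placebo rate.

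| Use | Model | Placebo | Probiotic | z | Power |
|---|---|---|---|---|---|
| 5% | placebo arm only | 24.375% | 12.5% | (1.502 − 1.075)/0.5420 = 0.788 | 78.5% |
| 10% | placebo arm only | 23.75% | 12.5% | (1.423 − 1.068)/0.5390 = 0.659 | 74.5% |
| 5% | both arms | 24.375% | 12.1875% | (1.542 − 1.071)/0.5398 = 0.871 | 80.8% |
| 10% | both arms | 23.75% | 11.875% | (1.502 − 1.061)/0.5345 = 0.826 | 79.6% |

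In the worst case, 1% or 2% use gives 81.3% or 80.7%, and power reaches 80% at 2.9% use (about 5 of 160).

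**6. Less extreme assumptions.** For a half-effective product (e = 0.25), 5% and 10% use give 80.3% and 78.5% with the placebo arm only, and 81.4% and 80.8% with both arms. If the placebo rate were the 34% seen per prescription in Stage 1, worst-case power at 10% use of a fully effective product would be 89.2%, and it would stay above 80% until 22.0% use.

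**7. Effect on the estimate.** In the worst case the apparent relative reduction is 1 − 12.5/24.375 = 48.7% at 5% use and 1 − 12.5/23.75 = 47.4% at 10%. Under the both-arms model the relative reduction stays at 50%, and only the absolute difference narrows: 12.5 points without use, 12.2 at 5% and 11.9 at 10%.

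**The case against.** The strongest reply has four parts.

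- **The sentence may not cover probiotics.** Section 11.6 follows sections on pre-medication and drug interactions, and the protocol calls probiotics dietary or nutritional supplements. This reading is fair, but it replaces permission with silence. A new start is still not barred.
- **Most of the risk is already handled, and uptake is not shown.** Regular users must discontinue, and medication after randomisation is recorded for eight weeks. The remark about commercial availability in Section 12.2.1 explains why not all adverse events are reported; it is not evidence that residents would buy such products. All of this stands and limits the size of the point. Recording describes use but does not prevent it, and whether the weekly form would pick up a shop-bought supplement cannot be told from the document.
- **Use confined to the placebo arm is a worst case.** Under blinding, uptake before any outcome should be similar in both arms. This stands, so the 78.5% and 74.5% figures are bounds rather than expectations.
- **An effectiveness trial may tolerate background use.** That is defensible in general, but it sits badly with excluding regular users who will not stop. Section 17.4 also reports that the regulator regards this as an efficacy study.

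A reader might infer that former regular users may resume. The text does not support this: discontinuing as a condition of entry is reasonably read as staying off. A reader might also infer that the trial is underpowered because of this gap. The document gives no rate of use from which to conclude that.

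**Conclusion.** The gap in the text is real. The entry checks protect a contrast that no rule protects after allocation, and it concerns residents who were not regular users at entry. For effective use in the placebo arm before a first AAD episode, the effect is to pull the intention-to-treat estimate towards no effect.

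The size is unknown and probably small. At assumed use of 5% to 10% of a fully effective product from the start, power falls from 82.0% to between 80.8% and 79.6% if both arms are affected alike, and to between 78.5% and 74.5% if only the placebo arm is. Use of 1% to 2% is negligible on either model. The 25% planning rate is itself a lower confidence limit, which leaves some margin. These figures rest on assumed use rates, a two-sided test, 160 evaluable per arm and no allowance for clustering.

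This is a cheap improvement of low to moderate priority. It is not a flaw that threatens the trial.

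**What to change.** Keep the sentence in Section 11.6 and add an exception to it:

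> *Exception: non-study probiotic supplements (not ordinary foods such as yoghurt) should not be started or resumed from allocation to the end of the eight-week follow-up. Participants who take one remain in follow-up and in the intention-to-treat analysis.*

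If the weekly Additional Medication form does not already prompt for it, add one item on non-study probiotic use (yes/no, with dates).

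The cost is a protocol amendment, a line in the information sheets, slightly more recording by care home staff and a minor restriction on residents. No one is excluded or withdrawn as a result, and the sample size and primary analysis stay as they are.
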